1.4.5. Overall Benefit/Risk Assessment

Based on the available data and proposed safety measures, the overall benefit/risk assessment for this study is acceptable for the following reasons:

-
- JNJ-63623872 has been studied in healthy subjects receiving single oral doses of JNJ-63623872 up to 1,600 mg (studies VX11-787-001 and VX12-787-002), multiple oral doses of JNJ-63623872 up to 800 mg once daily for 10 days (study VX11-787-001), multiple oral doses of JNJ-63623872 of 600 mg bid up to 10 days (study VX-787FLZ1001), and single IV doses of 100 mg JNJ-63623872 (study VX12-787-002), and in healthy subjects infected with a challenge dose of influenza A receiving multiple oral doses of JNJ-63623872 (up to 1,200 mg loading dose on the first day followed by 600 mg once daily for an additional 4 days) (study VX11-787-101). JNJ-63623872 was generally safe and well tolerated.
 - Only subjects who meet all of the inclusion criteria and none of the exclusion criteria (as specified in the protocol) will be allowed to participate in this study. The selection criteria include adequate provisions to minimize the risk and protect the well-being of subjects in the study.
 - Safety will be closely monitored by the investigator throughout the study. Safety and tolerability assessments (including vital signs, electrocardiogram [ECG], physical examination, clinical laboratory tests, and assessment of AEs or SAEs) will be performed at scheduled visits throughout the study.
 - Several safety measures have been proposed to minimize potential risks to subjects, including:
 - A safety management plan is in place for subjects experiencing specific toxicities such as allergic reactions, clinical hepatitis, renal complications, nausea, and diarrhea.
 - The safety margins for the projected exposures calculated from non-clinical toxicology studies in monkeys warrant close laboratory monitoring during the study, thus samples for clinical laboratory tests will be collected throughout the study. Elevations of liver enzymes (eg, AST, ALT, bilirubin, gamma-glutamyltransferase [GGT], alkaline phosphatase [ALP]), hematological changes, serum creatinine elevations, and presence of proteinuria/albuminuria will be closely monitored.
 - Utilization of withdrawal criteria (see Section 10.2).
 - Pregnancy and breastfeeding are exclusion criteria for all clinical studies conducted to date. All subjects are required to use contraceptive methods as detailed in the protocol.

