4.2. Exclusion Criteria

Any potential subject who meets any of the following criteria will be excluded from participating in the study.

1. Subject received more than 3 doses of the influenza antiviral medication oseltamivir, zanamivir, or peramivir since the start of the influenza symptoms, or ribavirin within 6 months prior to screening.
2. Subject is unwilling to undergo regular nasal MT swabs or has any physical abnormality which limits the ability to collect regular nasal specimens.
3. Subject is known (considering lab results of the past 6 months) to be severely immunocompromised as defined by a CD4⁺ count <350 cells/mm³ or an absolute neutrophil count <750/mm³.
4. Subject is undergoing peritoneal dialysis, hemodialysis, or hemofiltration.
5. Subject has an eGFR \leq 30 mL/min/1.73m² according to the MDRD equation, assessed at

screening or based on the most recent clinically relevant creatinine value if available.

6. Subject has known moderate (Child-Pugh class B) or severe hepatic impairment (Child-Pugh class C).
7. Subject has presence of any pre-existing illness, clinically significant laboratory abnormalities, ECG findings, or physical examination findings that, in the opinion of the investigator, would place the subject at an unreasonably increased risk through participation in this study. The investigator should consider the laboratory parameter criteria for study drug discontinuation (see Section 9.3.6) when screening a subject for enrollment.
8. Subject with known acute hepatitis A, B, or, C virus infection at screening, or known chronic hepatitis C infection undergoing antiviral therapy.
9. Subject has known allergies, hypersensitivity, or intolerance to JNJ-63623872 or its excipients (refer to the Investigator's Brochure⁶).
10. Subject has contraindications to the use of oseltamivir per local prescribing information.^{14,15}
11. Subject has received an investigational drug (including investigational vaccines) or used an invasive investigational medical device within 30 days, or has received an investigational biological product within 3 months or 5 half-lives (whichever is longer) before the planned first dose of study drug or is currently enrolled in an investigational study.
12. Subject has a history of clinically significant heart arrhythmias, eg, unstable angina or myocardial infarction; uncontrolled, unstable atrial arrhythmia, or sustained ventricular arrhythmia, or a history of risk factors for Torsade de Pointes syndrome.

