9.3.6. Specific Toxicities

Subjects reporting allergic reactions, AST/ALT elevations, clinical hepatitis, renal complications, nausea, or diarrhea, and other laboratory parameter changes should be followed until resolution of the AE or toxicity and necessary standard management should be undertaken.

Refer to Section [10.2](#) for study drug discontinuation criteria.

Acute Systemic Allergic Reaction

Cetirizine, levocetirizine, topical corticosteroids or antipruritic agents may be prescribed.

Subjects should be advised to contact the investigator immediately if there is any worsening of the acute systemic allergic reaction.

Subjects will be treated as clinically appropriate.

AST and ALT Elevation

Subjects should be followed until resolution (return to baseline) or stabilization of AST/ALT elevation (to be agreed upon with the sponsor).

Clinical Hepatitis

Subjects taking the study drugs should be monitored for the development of signs and symptoms of hepatitis which include fatigue, malaise, anorexia, nausea, dark urine and clay-colored stools, bilirubinuria, jaundice, liver tenderness, or hepatomegaly, with or without initially abnormal serum transaminase levels.

Subjects with these signs and symptoms must seek medical attention immediately and have hepatic parameters assessed. Relevant markers of viral hepatitis should also be assessed.

Renal Complications

If renal complications develop, subjects should be closely monitored for disturbances in serum creatinine and for abnormalities in urine analysis (eg, proteinuria). Additional investigations can be performed at the investigator's discretion. Subjects must be treated as clinically appropriate.

Nausea (with or without Vomiting)

Subjects may be treated as needed with antiemetics given orally or rectally. The date and time of this AE should be recorded.

Diarrhea

Loperamide can be administered.

Other Laboratory Parameter Changes

If one (or more) of the following changes occurs, the subject should discontinue study drug and should be followed until resolution (return to baseline) or stabilization of change (to be agreed upon with the sponsor). The sponsor should be informed even if the change occurs outside of the treatment period (but before the end of the study).

- Liver enzymes - *screening/baseline*
 - AST or ALT enzyme activity increases ≥ 5 x ULN
 - Direct bilirubin increases ≥ 2 x ULN
 - GGT and/or ALP enzyme activity increases ≥ 3 x ULN

- Liver enzymes - *during treatment*

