 - AST or ALT enzyme activity increases ≥ 5 x ULN if the baseline value is normal
 - AST or ALT enzyme activity increases ≥ 5 x baseline if the baseline value is $>ULN$
 - ALT enzyme activity increases >15 x ULN
 - ALT enzyme activity increases >3 x ULN and total bilirubin increases >2 x ULN
- Confirmed absolute neutrophil count $<500/mm^3$
- Hemoglobin <9 g/dL (female), <10.5 g/L (male)

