10.2. Discontinuation of Study Treatment

If a subject's study treatment must be discontinued before the end of the treatment regimen, this will not result in automatic withdrawal of the subject from the study.

A subject's study treatment should be discontinued if:

- The investigator believes that for safety reasons (eg, AE) it is in the best interest of the subject to discontinue study treatment
- The subject becomes pregnant
- The subject undergoes mechanical ventilation
- The subject requires peritoneal dialysis, hemodialysis, or hemofiltration
- The subject has an eGFR ≤ 30 mL/min/1.73 m² according to the MDRD equation
- The subject experiences any of the laboratory abnormalities as specified in Section [9.3.6](#), Specific Toxicities.

If a subject prematurely discontinues study treatment, follow-up assessments should be obtained and scheduled assessments should be continued. If a subject drops out due to withdrawal of consent, he or she will be offered an optional Safety Follow-up Visit.

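### The male haemoglobin stopping limit in Protocol 9.3.6 is printed in g/L; taken literally it is 1.05 g/dL, so the numeric stop cannot work for men

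*Protocol*

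**What the plan says.** The haemoglobin limit is the last entry under Other Laboratory Parameter Changes in Protocol 9.3.6: "Hemoglobin <9 g/dL (female), <10.5 g/L (male".

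The lead-in to that list states what follows when a limit is met: "If one (or more) of the following changes occurs, the subject should discontinue study drug and should be followed until resolution" or stabilization. It adds a reporting duty: "The sponsor should be informed even if the change occurs outside of the treatment period", provided the study has not ended.

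Two other sections rely on the list without giving a haemoglobin figure of their own:

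- Section 10.2 makes it a reason to discontinue treatment: "The subject experiences any of the laboratory abnormalities as specified in Section" 9.3.6.
- Exclusion criterion 7 in Section 4.2 brings it into screening: "The investigator should consider the laboratory parameter criteria for study drug discontinuation (see Section 9.3.6) when screening a subject for enrollment".

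Section 1.4.5 names both the laboratory monitoring ("hematological changes, serum creatinine elevations, and presence of proteinuria/albuminuria will be closely monitored") and the Section 10.2 withdrawal criteria among the measures that make the risk acceptable.

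**The concern.** A single line uses two units that differ by a factor of ten. Read as printed, the male limit is so low that it would never act, while the female limit beside it is an ordinary clinical threshold.

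The line triggers three things: stopping study drug, following the subject to resolution or stabilization, and informing the sponsor. On a literal reading none of these is triggered by a number for a man. The same unusable limit is also what an investigator is told to consider when screening a man. Because Section 10.2 and exclusion criterion 7 only point back to 9.3.6, neither gives a site a second figure to check against.

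**Working it through.** There is no derived figure to reproduce. The check is a unit conversion, followed by a comparison with the documents' own haemoglobin grades.

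**Inputs**

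- Female limit: <9 g/dL; male limit: <10.5 g/L (Protocol 9.3.6).
- Haemoglobin grades: Grade 1, 9.5-10.5; Grade 2, 8.0-9.4; Grade 3, 6.5-7.9; Grade 4, <6.5. All are in gm/dL with no split by sex (Protocol Attachment 1, repeated in SAP Appendix 2).
- Conversion: 1 g/dL = 10 g/L.

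**Conversion**

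- Male limit as printed: 10.5 g/L ÷ 10 = 1.05 g/dL.
- Male limit if g/dL was meant: 10.5 g/dL = 105 g/L. Ratio to the printed limit: 10.5 ÷ 1.05 = 10.
- Printed male limit against the Grade 4 cut-off: 1.05 ÷ 6.5 = 0.16.
- Female limit against the printed male limit: 9 ÷ 1.05 = 8.6.

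**Who meets the stop**

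| Haemoglobin (g/dL) | Grade | Man, as printed | Man, if g/dL | Woman, as printed |
|---|---|---|---|---|
| 10.4 | 1 | no | yes | no |
| 9.4 | 2 | no | yes | no |
| 8.0 | 2 | no | yes | yes |
| 7.9 | 3 | no | yes | yes |
| 6.4 | 4 | no | yes | yes |
| 5 | 4 | no | yes | yes |
| 3 | 4 | no | yes | yes |
| 1.04 | 4 | yes | yes | yes |

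The two readings of the male rule disagree for every value from 1.05 to just under 10.5 g/dL. That range covers Grade 1 below 10.5, all of Grades 2 and 3, and Grade 4 down to 1.05. For example, a man at 7.0 g/dL (Grade 3) does not meet the printed stop, whereas a woman at 8.9 g/dL (Grade 2) does.

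**When the rule would be applied**

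In the Time and Events Schedules, on-treatment haematology after baseline falls on Days 3 and 5 in hospital, or on Day 5 after discharge. Further samples on Days 10 and 28 bear on the reporting duty, which continues after treatment.

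**Is it corrected elsewhere?**

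No. Section 10.2 and exclusion criterion 7 only refer back. The grading tables show the unit in use but set no stopping limit.

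**The case against.** The strongest reply is that this is a self-evident typing error with little practical effect.

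- **The intended unit is obvious.** It appears earlier on the same line, and 10.5 gm/dL is a printed grade boundary in Attachment 1. A limit of 1.05 g/dL is not credible, so few sites would apply it.
- **Other provisions cover much of the ground.** Section 10.2 keeps the investigator's own stop: "The investigator believes that for safety reasons (eg, AE) it is in the best interest of the subject to discontinue study treatment". The opening paragraph of 9.3.6 asks for follow-up of laboratory changes without any numeric threshold. Section 9.3.2 allows a confirmatory test for Grade 3 or 4 values and requires the investigator to review each report. Section 17.6 sends central laboratory data directly to the sponsor's database. An independent committee reviews interim data (Section 11.8).
- **Exposure is short.** Treatment is 14 doses, and only about two dosing days remain after the Day 5 sample.
- **A letter might have been lost in converting the PDF to text.**

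Most of this stands as a limit on the harm. Follow-up and the sponsor's sight of the values have partial cover elsewhere, and the literal reading is unlikely at most sites. It does not remove the defect. None of those provisions supplies a numeric stop for men, and data reaching the sponsor's database does not replace the site's duty to notify. A stopping limit in a multicentre trial should not depend on each site guessing the unit. Loss of a letter in conversion is unlikely, because g/dL is intact earlier in the same line.

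**Conclusion.** The concern holds. As printed, the male limit is 1.05 g/dL, a tenth of the likely intended 10.5 g/dL, and it cannot act as a numeric stop.

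This rests on one assumption: that g/dL was meant. The female limit and both grading tables make that very probable. The practical effect is confined to men whose haemoglobin lies between 1.05 and just under 10.5 g/dL, at sites that take the unit literally. The documents give no expected frequency of such values, so the number of subjects affected cannot be estimated.

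No endpoint, sample size or SAP analysis is touched. It should be fixed because it is a wrong threshold in a live safety rule, even though discretion to stop remains.

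**What to change.** Change the male unit so that the entry reads: haemoglobin <9 g/dL (female), <10.5 g/dL (male).

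Before issuing it, the sponsor should confirm that 10.5 g/dL is the value wanted. At that level a man stops at the upper edge of Grade 1 (9.5-10.5 gm/dL), while a woman at 9 g/dL stops within Grade 2 (8.0-9.4 gm/dL). A sex-specific limit may well be deliberate, but the haemoglobin entry, unlike the on-treatment AST/ALT entries, makes no allowance for an abnormal baseline. A man who enters the study just under 10.5 g/dL would therefore meet the corrected rule at once.

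Section 10.2 and exclusion criterion 7 take their limits from 9.3.6 and need no edit. The cost is a one-line protocol correction or a clarification letter to sites.

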9.4. Efficacy

9.4.1. Evaluations

9.4.1.1. Patient-reported Outcomes

Subjects should complete the PRO assessments (Flu-iiQ™, Flu-PRO and additional daily diary items) in their native language or if there is no version available in their native language, a version in a language in which the subject is fluent and literate. It is preferable that subjects are able to read and write to complete the assessments by themselves. If a subject is unable to read or has visual or other physical limitations that make it difficult to read or complete the assessments, trained study personnel may read the questions and responses aloud exactly as they appear on the assessment and record the subject's responses during the hospitalization phase. Once the subject is discharged from the hospital, if the subject is unable to complete the PRO assessment unaided, a caregiver can read the questions and responses verbatim and record the subject's responses for the subject.

Study personnel will instruct subjects how to self-administer the PRO tool and will record in the eCRF whether the PRO assessments were performed during the study visit. If subjects will require assistance recording their responses post-hospital discharge, study personnel will instruct the caregiver how to administer the PRO assessments.

Subjects will complete the PRO assessments electronically on a touch screen computer (ePRO device) provided for this study. The subject should be provided a quiet place to complete the PRO assessments, and instructed how to complete the PRO assessment on the ePRO device. When deciding which answer to report, subjects should not receive any help from anyone accompanying them (such as family members and friends) or study personnel; the responses should reflect the subject's interpretation and response.

Subjects' responses to the PRO questionnaires will not be reported as AEs or SAEs.

Influenza Symptom Score (Flu-iiQ™ Module 1)

Subjects will be asked to assess influenza-related signs and symptoms and other patient-reported outcomes and associated severity twice daily (preferably in the morning and in the evening) from study entry (Baseline, Day 1) through Day 14, and once daily (preferably in the evening) from

Day 15 through the Final Study Visit/Safety Follow-up Visit, using the Flu-iiQ™ influenza intensity and impact questionnaire (see [Attachment 3](#)) on an ePRO device.

Assessment of influenza symptoms will be recorded by the subjects or the site staff/caregiver if the subject requires assistance on the ePRO device and analyzed as an efficacy measure of treatment. Resolution of influenza symptoms will be the time since the start of treatment of the first of 2 evaluations (over 24 hours) in which all symptom scores for each of the 2 assessments are none or mild for all 7 primary influenza symptoms (cough, sore throat, headache, nasal stuffiness, feverishness or chills, muscle or joint pain, and fatigue).

Impact of Influenza (Flu-iiQ™ Modules 2, 3, 4)

The impact of influenza on conduct of daily activities will be assessed in Module 2 of the Flu-iiQ™ (see [Attachment 3](#)), scored on a 4-point scale, as above, for each of 6 activities. Scores will be assessed twice daily, at the same times as when the symptom scale evaluation is performed, from study entry (Baseline, Day 1) through Day 14, and once daily from Day 15 through the Final Study Visit/Safety Follow-up Visit. Assessments along with the additional daily diary items (see [Attachment 4](#)) will be recorded on the ePRO device. Time to resumption of usual activities is the time at which all scores are reported as “no difficulty”.

Flu-PRO

The incidence and severity of symptoms (individual and composite) will be evaluated using the Flu-PRO questionnaire (see [Attachment 5](#)). Subjects will be asked to complete this questionnaire and additional daily diary items (see [Attachment 6](#)) on an ePRO device once daily (preferably in the evening) from study entry (Baseline, Day 1) through the Final Study Visit/Safety Follow-up Visit.

9.4.1.2. Viral Kinetics (Nasal MT Swabs)

Influenza viral titer will be determined and quantified in nasal MT swab samples taken at scheduled times throughout the study as indicated in the [TIME AND EVENTS SCHEDULE](#). Nasal MT swabs will be analyzed using qRT-PCR and/or viral culture, and PCR-based rapid molecular testing. Influenza A subtype will be determined from the baseline sample.

When subjects are discharged from the hospital and still positive for influenza A virus, they are encouraged to continue self-swabbing at home if practically feasible.

Details about the nasal MT (self-) swab sample collection, processing, and shipping will be provided in the laboratory manual or other instruction documents.

The nasal MT swabs for central testing should be obtained from the left and the right nostrils and pooled into the same collection tube. Nasal MT (self)swabs for local PCR-based rapid molecular testing should be obtained from the left and the right nostrils (from both nostrils if feasible, but from only one nostril otherwise) and pooled into the same collection tube. Sampling should be done at approximately the same time when required. The investigator should designate a limited

number of trained study site personnel to collect the nasal MT swabs for the sake of consistency, and to train subjects on how to collect self-swabs if applicable.

9.4.2. Efficacy Endpoints

The efficacy endpoints, being the secondary endpoints of this study are listed in Section 11.6.

9.5. Resistance Evaluations

9.5.1.1. Viral Sequencing

Samples collected as described in Section 9.4.1.2 will also be used for sequence analysis of the PB2 region of the influenza virus polymerase and the neuraminidase gene at the time points specified in the [TIME AND EVENTS SCHEDULE](#). Exploratory sequencing of other regions of the influenza virus genome may also be performed.

9.5.1.2. Phenotyping

Nasal MT swabs will be used for the analysis of phenotypic resistance against JNJ-63623872 and other antivirals at the time points specified in the [TIME AND EVENTS SCHEDULE](#).

Details about sample collection, processing, and shipping will be provided in the laboratory manual.

9.6. Biomarkers

Two blood samples will be collected at the time points specified in the [TIME AND EVENTS SCHEDULE](#) for the exploration of blood biomarkers (eg, host RNA, proteins including serum cytokines) on the premise that these markers may play a role in the blood concentrations, treatment response, or safety of JNJ-63623872 or oseltamivir, or the status and change of the influenza virus related disease. Where local regulations permit, an optional blood sample may be collected for host DNA genotyping.

In addition, nasal MT swabs collected for other testing may be used for biomarker analyses if available.

Analyses of biomarkers (including DNA) may be conducted at the sponsor's discretion and reported separately from this study.

Blood samples for pharmacogenomic evaluations will preferably be collected at the baseline visit. However, if necessary eg, in case of a technical failure, they may be collected at a later time point without constituting a protocol deviation.

9.7. Sample Collection and Handling

The actual dates and times of sample collection must be recorded in the eCRF or laboratory requisition form. If blood samples are collected via an indwelling cannula, an appropriate amount (1 mL) of serosanguineous fluid slightly greater than the dead space volume of the lock will be removed from the cannula and discarded before each blood sample is taken. After blood

sample collection, the cannula will be flushed with 0.9% sodium chloride, United States Pharmacopeia (USP) (or equivalent) sodium heparin of 10 U/mL and charged with a volume equal to the dead space volume of the lock.

Refer to the [TIME AND EVENTS SCHEDULE](#) for the timing and frequency of all sample collections.

Instructions for the collection, handling, storage, and shipment of samples are found in the laboratory manual that will be provided. Collection, handling, storage, and shipment of samples must be under the specified, and where applicable, controlled temperature conditions as indicated in the laboratory manual.

